CI	Confidence Intervals
CT	Chlamydia trachomatis
CSR	Clinical Study Report
eCRF	Electronic Case Report Form
g	Gram
GC	Neisseria gonorrhoeae
GCP	Good Clinical Practice
uHCG	(urine) Human Chorionic Gonadotropin
HIPAA	Health Insurance Portability and Accountability Act
HR	Heart Rate
ICH	International Conference on Harmonisation
ITT	Intent to Treat
MedDRA [®]	Medical Dictionary for Regulatory Activities
N	Number (typically refers to subjects)
PP	Per Protocol
SAE	Serious Adverse Event/Serious Adverse Experience
SMC	Safety Monitoring Committee
SOC	System Organ Class
TEAE	Treatment Emergent Adverse Event
TOC	Test of Cure
WHO	World Health Organization

1 INTRODUCTION

The purpose of this Statistical Analysis Plan (SAP) is to provide detailed descriptions of the statistical methods, data derivations and data displays for study protocol EVO-003 Version 6.0 “Phase 2B/3 double-blinded placebo-controlled efficacy trial of AMPHORA[®] gel for the prevention of acquisition of urogenital Chlamydia trachomatis infection” dated 25JAN2019 for CSR analysis. The table of contents and templates for the TFLs will be produced in a separate document.

Any deviations from this SAP will be described and justified in the Clinical Study Report (CSR).

The preparation of this SAP has been based on International Conference on Harmonisation (ICH) E9.

All data analyses and generation of TFLs will be performed using SAS version 9.4 or higher on the SAS Grid.

2 STUDY OBJECTIVES

2.1 Primary objective

To determine if intravaginal AMPHORA gel reduces the risk of urogenital *Chlamydia trachomatis* (CT) infection.

2.2 Secondary objective

To determine if intravaginal AMPHORA gel reduces the risk of urogenital *Neisseria gonorrhoeae* (GC) infection.

2.3 Exploratory objective

To determine if AMPHORA gel use rate (subject adherence to instructed use) has an effect on proportion of subjects who experience at least one CT or GC infection during the study intervention period.

To assess subject satisfaction (including sexual satisfaction) with AMPHORA gel over the course of the clinical trial.

3 STUDY DESIGN

3.1 General study design

Eight hundred forty-four (844) women, ages 18-45, who have had a documented urogenital infection at any time over 16 weeks (up to 118 days) preceding the enrollment visit, or found to be positive at screening visit will be enrolled. Subjects will be tested for current GC/CT infection by NAAT (vaginal swab).

A baseline vaginal pH and a full gynecologic exam (speculum) will be obtained at enrollment. Those who test positive for CT/GC infection at screening will receive standard of care (SOC) treatment. To meet eligibility criteria, these subjects will not be enrolled until 3-4 weeks after screening (at least 21 days after treatment).

Subjects are instructed to apply AMPHORA or placebo gel up to one hour prior to coitus for the duration of the 16-week intervention period. AMPHORA or placebo is to be reapplied in the same manner for each occurrence of sexual intercourse. Subjects will keep an electronic diary (eDiary) to document and track sexual activity and product use and condom use.

Every 4 weeks (5 visits) all subjects will return to the clinic for repeat CT/GC NAAT (vaginal swab), urine pregnancy (uHCG) testing, eDiary review, and return of used and unused study product. Applicators will be visually inspected for use and staining will be performed to confirm vaginal insertion of used (empty) applicators. At each Visit 2-4, subjects will be re-supplied with AMPHORA or placebo gel. At Visit 5, subjects will return used and unused study product and continue to use their e-diaries but will not be resupplied with AMPHORA or placebo gel.

Subjects will return for a follow-up visit four weeks after the intervention period. At this time, a repeat CT/GC NAAT (vaginal swab), pregnancy (uHCG) testing and eDiary review will be performed.

Screening and Eligibility

Subjects who consent may be screened if they have a known case of CT or GC within 16 weeks of enrollment, or suspicion of current CT or GC infection (subsequently confirmed with NAAT test at screening visit). Subjects randomized within 45 days of initial screening do not need to be re-screened.

Intervention and Follow-up Period

The Intervention Period is defined as Visit 1 through Visit 5. There is one follow-up visit (Visit 6), four weeks after the last intervention visit. These periods are outlined in the Schedule of Assessments. The protocol defined period of observation is 20 weeks.

Safety Follow-up After Protocol Defined Period of Observation

This period includes safety follow-up as required by Good Clinical Practice and standard clinical trial practice. Adverse events determined to be at least possibly related to the study product

continuing after the final study visit (Visit 6) will be followed until resolution or stable status as determined by the Investigator.

3.2 Randomization and blinding

This is a Phase 2B/3 placebo-controlled randomized trial, with 422 subjects per intervention arm; for a total of 844 subjects to be enrolled. The 844 subjects will be randomized using an Interactive Web Interactive System (IWRS), in a 1:1 fashion across the two intervention groups, IP or placebo. Simple randomization will be stratified by site and all documentation of this procedure will be saved with the IWRS vendor until the end of the study. Randomization will occur following enrollment and prior to issuance of study product to subjects.

On completion of the trial, after data entry is complete and the data is considered to be clean, the final database will be locked and the study will be fully unblinded.

3.3 Study treatments and assessments

Approximately 24 weeks: Screening, five intervention period visits (one every 4 weeks) and one post-intervention follow-up visit (4 weeks after the last intervention period visit). Following screening, enrollment and randomization, subjects will be issued a 4-week supply of study product based on the individual subject's projected usage. During the Intervention Period, subjects will return all unused product and used applicators packaged individually in plastic return bags provided, and be issued a new 4-week supply of study product based on projected usage. Subjects may be issued additional study product, as needed, should their supply be exhausted prior to the next study visit; however, excessive product usage should be brought to the attention of the Investigator and Sponsor. At Visit 5, subjects will return all unused product and used applicators.

Table 1 shows the study dosing for each intervention group.

Table 1: Investigational Product Dosing

Intervention Group	IP: AMPHORA gel*	Placebo: Universal Placebo Gel*
Group A	422 subjects, 5 g dose applied up to 1 hour prior to coitus**	N/A
Group B	N/A	422 subjects, 5 g dose applied up to 1 hour prior to coitus**

*The dosage of study product is 5 g (as described for each intervention group) in a pre-filled vaginal applicator.

**A detailed description of procedures and assessments to be conducted during this study is summarized in the Scheduled of Study Assessments in Table 2 below.

Table 2: Schedule of Study Assessments

Study Visit (V)	Screening ⁽¹⁾	Intervention Period; AMPHORA gel N=422, Placebo gel N=422					Post-Intervention Follow-up/Visit 6
		Enrollment/ Visit 1 ⁽²⁾	Visit 2 ⁽²⁾	Visit 3 ⁽²⁾	Visit 4 ⁽²⁾	Visit 5 ⁽²⁾	
Study Week	-4 – 0 (-30 – 0 days)	0	4	8	12	16	20
Study Product Dispensed		X	X	X	X		
Informed Consent/HIPAA	X						
Inclusion/Exclusion	X	X					
Concomitant Meds	X	X	X	X	X	X	X
AE Assessment		X	X	X	X	X	X
Medical/Sexual History	X	X					
Last Menstrual Period		X					
Physical Exam		X					
Targeted Physical Exam			[X]	[X]	[X]	[X]	[X]
Body Weight/Height		X					
Vital Signs		X					
Gynecologic Exam		X					
Urine HCG (females)		X	X	X	X	X	X
Vaginal pH		X					
Self-collected CT/GC NAAT	X		X	X	X	X	X
Clinician-collected CT/GC NAAT		X					
eDiary Set-up		X					
eDiary Review			X	X	X	X	X
Inspection of Returned Study Product			X	X	X	X	
Staining of Used Applicators			X	X	X	X	
Subject Satisfaction With Product						X	
Subject Sexual Satisfaction						X	
Female Sexual Function Index (FSFI)		X				X	
Sexual Function Questionnaire		X				X	

⁽¹⁾ Screening period may be up to 45 days. Subjects will be asked to return 7 days +/- 7 days after Screening Visit. If subjects NAAT results are positive, they will be first treated by SOC then will return 3 – 4 weeks after screening visit (at least 21 days after treatment) for Enrollment/Visit 1. If the screening period extends past 45 days, subjects will not be enrolled and will need to be re-screened.

⁽²⁾ Patients must be asked to abstain from vaginal intercourse in the 24 hours preceding study visits 2 through 5.

4 STUDY ENDPOINTS

4.1 Primary efficacy endpoint

The primary efficacy endpoint is the proportion of subjects who experience at least one urogenital CT infection during the study intervention period (incident infection of CT).

4.2 Secondary efficacy endpoint

The secondary efficacy endpoint is the proportion of subjects who experience at least one urogenital GC infection during the study intervention period (incident infection of GC).

4.3 Exploratory endpoints

Exploratory endpoints will comprise:

- Adherence with AMPHORA gel usage during study (rate of product use adherence).
- Sensitivity analyses of the primary and secondary parameters will be performed for the following:
 - mITT Subjects with $\geq 20\%$, $\geq 40\%$, $\geq 60\%$, $\geq 80\%$, and 100% product use adherence.
 - Re-infection rate analysis with alternative definition of no re-infection
- Subject satisfaction
- Sexual satisfaction

5 SAMPLE SIZE AND POWER

The primary analysis is a comparison between proportion of subjects who experience at least one CT infection among the intervention groups (AMPHORA or placebo).

It is assumed that the proportion of patients experiencing at least one infection of CT during the study period (incident infection of CT) up to week 16 under placebo will be 22.5%. An incident infection of CT of 13% in the patients receiving active treatment (i.e., a treatment difference of 9.5%) is considered clinically relevant for AMPHORA versus placebo. Using a Chi-Square Test for the primary endpoint, 253 analyzable patients per treatment group (506 patients total in the ITT population) will yield approximately 80% power to detect 9.5% treatment difference with a 2-sided 5% type I error rate (SAS 9.3 PROC POWER). Assuming that 20% of the total enrolled patients will be lost to follow-up, 15% will be re-infected with GC (making them ineligible for the primary endpoint analysis), and 5% will be deemed ineligible for analysis due to antibiotic use, the total sample size planned for this study is 844 patients.

6 ANALYSIS POPULATIONS

This study will utilize three analysis populations: Intention-to-Treat (ITT), modified Intention-to-Treat (mITT), and safety.

6.1 Intention-To-Treat population (ITT)

The ITT population is defined as all randomized subjects. Analyses with this population will be performed based on the treatment randomized.

6.2 Modified Intention-To-Treat population (mITT)

The modified ITT population is defined as all randomized subjects who report use of study product (IP or UPG) and have negative GC/CT test result at enrollment. Analyses with this population will be performed based on the treatment randomized.

6.3 Safety population (Safety)

All randomized subjects who applied any amount of study product will be included in the Safety population. Analysis with this population will be performed based on the treatment actually received.

6.4 Protocol deviations/violations and exclusions from analysis sets

A cumulative list of protocol deviations will be reported in the Clinical Study Report.

7 STATISTICAL CONSIDERATIONS AND ANALYSIS

7.1 Derived Variables

The below table provides a list of derived variables for demographic and baseline characteristics.

Variables	Formula
Demographic and Baseline characteristics	
Age at informed consent (in years)	integer ((date of informed consent – date of birth + 1)/ 365.25)
Body mass index (BMI) (kg/m ²)	weight (kg)/[height (m)] ²

7.3 Analysis Eligible Subjects

When considering subjects for inclusion in the re-infection analyses, it becomes apparent that some are not appropriate for consideration. As an example, if a subject is treated with an antibiotic for an illness and this antibiotic also treats GC and/or CT, then it is not possible to get a true reflection as to the re-infection prevention abilities of the product under investigation. Likewise, if a subject is found to be infected with GC and needs to be treated, the ability to later detect a CT infection is compromised. As such, for subjects to be eligible for CT (or GC) re-infection analyses, we require the following:

- 1) Known re-infection status through the end of the treatment phase (i.e., a determination of positive or negative re-infection can be definitively made per definitions below),
- 2) No use of prohibited antibiotic medications, and
- 3) No GC (or CT) re-infection, unless it is identified at the same time as the CT (or GC) re-infection.

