#### Exploratory:

- Compliance with AMPHORA usage during study (rate of product use adherence)
- Sensitivity analyses of the primary parameter (proportion of subjects who experience at least one CT or GC infection during the study intervention period) will be performed for the following:
  - o Subjects with  $\geq 20\%$ ,  $\geq 40\%$ ,  $\geq 60\%$ ,  $\geq 80\%$  and 100% product use adherence
- Subject satisfaction
- Sexual satisfaction

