#### 8.2 Sample Size Considerations

The primary analysis is a comparison between proportion of subjects who experience at least one CT infection among the intervention groups (AMPHORA or placebo).

It is assumed that the proportion of subjects experiencing at least one infection of CT during the study period (incident infection of CT) up to Week 16 under placebo will be 22.5%. An incident infection of CT of 13% in the subjects receiving active treatment (ie, a treatment difference of 9.5%) is considered clinically relevant for AMPHORA versus placebo. Using a Chi-square test for the primary endpoint, 253 analyzable subjects per treatment group (506 subjects total in the ITT population) will yield approximately 80% power to detect 9.5% treatment difference with a 2-sided 5% type I error rate (SAS 9.3 PROC POWER). Assuming that 20% of the total enrolled subjects will be lost to follow-up, 15% will be re-infected with GC (making them ineligible for the primary endpoint analysis), and 5% will be deemed ineligible for analysis due to antibiotic use, the total sample size planned for this study is 844 subjects.

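### GC-positive women can enter the CT analysis only as CT cases, so a gel effect on GC alone can bias the primary CT comparison, in a direction that is not fixed

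*SAP*

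**What the plan says.** SAP 7.3 sets three conditions for entering the CT analysis. The third rules out a woman with a GC re-infection, "unless it is identified at the same time as the CT (or GC) re-infection". The reason given is that "if a subject is found to be infected with GC and needs to be treated", a CT infection arising afterwards may be missed.

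SAP 8.8.1 takes the primary denominators from this eligible subset of the mITT population. A non-case must be NAAT-negative at Visits 1 and 5 with no positive result between. Protocol 8.3.3 has the same structure: it analyses women infected with CT plus women who finish free of both infections. Protocol 8.2 plans for the loss, assuming that "15% will be re-infected with GC (making them ineligible for the primary endpoint analysis").

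GC prevention is the secondary objective (Protocol 1.3, SAP 2.2). The exploratory outcomes in the Protocol Synopsis name the "proportion of subjects who experience at least one CT or GC infection during the study intervention period", but SAP 8.8.3 tests CT and GC separately. Its alternative definition of no re-infection only adds one more required negative visit and leaves the GC exclusion in place.

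**The concern.** A woman who is GC-positive and CT-negative at a visit has a known CT-negative record up to that visit, yet she is removed altogether. A woman positive for both at that visit is kept as a CT case. Non-cases must also stay free of GC until Visit 5, while CT cases need not.

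Eligibility therefore depends on something that happens after randomisation and that the gel is meant to change. If GC falls on the gel, fewer women leave the active arm than the placebo arm, and the two analysed groups are no longer the groups that were randomised. The primary CT proportions can then differ although the gel does nothing for CT. What is at stake is the type I error of the primary test and the size of the reported CT effect.

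**Working it through.** **Inputs from SAP section 5.** Placebo CT risk: "up to week 16 under placebo will be 22.5"%. Active: "An incident infection of CT of 13% in the patients receiving active treatment". The test is made "with a 2-sided 5% type I error rate". Precision: "253 analyzable patients per treatment group (506 patients total in the ITT population) will yield approximately 80% power". GC re-infection is 15%, stated as a share of all enrolled women and used here as the placebo rate.

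**Assumed, because the documents give no figure.** GC risk on the gel of 8.7% or 5%; the association between CT and GC; 253 analysed per arm (the plan) up to 330.

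**The plan's own figure.** For 22.5% vs 13%, pooled variance and no continuity correction, n = 252.8, so 253 per arm, with power 0.800. Losses of 20% + 15% + 5% = 40% give 253/0.60 = 421.7, so 422 per arm and 844 in total. The stated sample size reproduces.

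**Model.** Four post-baseline visits, constant risk per visit, exit at first infection.
- Risk per visit: h = 1 - (1 - p)^(1/4).
- Free of both at Visit 5: F = (1 - p_CT)(1 - p_GC).
- CT cases, including those found with GC at the same visit: C = h_CT × (1 - F)/(1 - F^(1/4)).
- Analysed CT proportion under rule 3: C/(C + F).

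**No CT effect (22.5% in both arms), CT and GC independent.** Here h_CT = 1 - 0.775^(1/4) = 0.0617.

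| GC risk | F | C | Removed as GC-only | C/(C + F) |
|---|---|---|---|---|
| 15% (placebo) | 0.775 × 0.85 = 0.6588 | 0.2126 | 12.9% | 0.2440 |
| 8.7% (active) | 0.775 × 0.913 = 0.7076 | 0.2179 | 7.5% | 0.2355 |
| 5% (active) | 0.775 × 0.95 = 0.7363 | 0.2210 | 4.3% | 0.2308 |

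The false benefit is 0.2440 - 0.2355 = 0.0085 (about 0.9 points) or 0.2440 - 0.2308 = 0.0132 (1.3 points). For 253 to 330 per arm these are shifts of 0.22-0.26 or 0.35-0.40 standard errors. Two-sided error is 5.6-5.8% or 6.4-6.8%. With active GC also 15%, the difference is 0 and the error 5.0%.

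**At the planned CT effect.** The analysed difference is 10.2, 10.7 or 11.0 points for active GC of 15%, 8.7% or 5%, against 9.5 planned.

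**Clustering.** Now let both risks fall only on a fraction f of women, each risk being p/f within that fraction, with the overall risks unchanged, no CT effect, and GC 15% vs 8.7%. At f = 0.5, placebo has C = 0.2011 and F = 0.6925, so 0.2250; active has C = 0.2116 and F = 0.7271, so 0.2254. The last column keeps GC-only women and censors them at the GC visit (Kaplan-Meier). Positive values favour the gel.

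| Fraction at risk | Rule 3, points | Censored at GC, points |
|---|---|---|
| 100% (independence) | +0.9 | 0.0 |
| 80% | +0.6 | -0.2 |
| 60% | +0.25 | -0.45 |
| 50% | 0.0 | -0.7 |
| 40% | -0.4 | -1.0 |

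The sign turns because women spared GC stay under observation and, being the women at risk, some later become CT cases.

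**The case against.** The exclusion has a stated clinical reason, and the 15% loss is already built into the 844. It will also be visible: SAP 8.2 and 8.3 tabulate the eligible women and the reasons for exclusion by arm, and SAP 8.8.2 compares GC directly. All of this stands. But a visible imbalance does not show what it did to the CT result. The stated reason supports ending CT follow-up at the GC visit, not discarding the CT-negative results already obtained.

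A reader might infer that the primary result is biased toward the gel whenever the gel lowers GC. The documents do not support that. It needs CT and GC to be roughly independent within arm, and nothing in the plan says so. Both infections are sexually acquired, and the trial enrols women at high risk of re-infection, so clustering is plausible.

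A reader might also infer that rule 3 should be replaced by censoring in the primary analysis. The clustering table argues against this: from 60% downward, censoring has the larger absolute bias. Replacement would also overturn the chi-square test, evaluable set and sample-size basis in Protocol 8.2, 8.3.3 and 8.4.1.

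Finally, the exploratory wording on CT or GC may be shorthand for each infection in turn, since SAP 4.3 refers to the primary and secondary parameters. On that reading no promised analysis is missing. The gap remains, because no analysis in the text available keeps GC-only women in the CT comparison. SAP 7.2, on missing data, was not available for this check.

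**Conclusion.** The concern holds in a limited form. Rule 3 of SAP 7.3, with Protocol 8.3.3, makes the primary CT analysis set depend on GC, an outcome the trial tests as an effect of the gel. A GC effect can therefore move the CT comparison with no CT effect.

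The size is modest: about 0.9 to 1.3 points in the gel's favour under independence and the assumed GC rates, falling to zero and then reversing as the infections cluster. If GC is unaffected there is no bias. A shift of this size could not by itself produce the planned 9.5 points, but it can take the two-sided error above 5%.

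One ambiguity does not alter this. A woman with CT first and GC at a later visit is excluded on a literal reading of SAP 7.3 and kept under Protocol 8.3.3. On either reading, no woman with a GC re-infection counts as a CT non-case.

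**What to change.** Keep the planned chi-square analysis as primary. Add two supportive analyses in the mITT population to SAP 8.8.3:

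- **(a) CT cumulative incidence to Week 16**, with GC-only women retained and censored at their first GC-positive/CT-negative visit. State that antibiotics given for that GC infection, and the resulting lack of a Visit 5 status, do not remove these women under rules 1 and 2 of SAP 7.3. State also that censoring assumes GC is uninformative for CT within arm.
- **(b) First CT or GC infection as a composite**, with no exclusion for GC. The exploratory objective already names this outcome. It avoids the exclusion, but it neither isolates a CT effect nor tests the censoring assumption in (a), and a GC-only effect enters it in full.

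Add a sentence to SAP 8.8.1 saying that the primary CT result will be read alongside the number of GC exclusions in each arm and these two analyses.

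The NAAT data for both organisms are already collected at each visit (Protocol 5.6.3), so no visit, sample or patient management changes. The cost is a little extra programming and two more supportive results to report and explain.

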8 STATISTICAL METHODS

8.1 General statistical conventions

All statistical procedures will be completed using SAS version 9.4 or higher on the SAS Grid.

Unless otherwise stated, all statistical testing will be two-sided and will be performed using a significance (alpha) level of 0.05. Two-sided 95% confidence intervals (CI) will be provided when relevant.

For continuous variables, descriptive statistics will include the number of non-missing values, mean, standard deviation, median, minimum, and maximum. For categorical variables, descriptive statistics will include counts and percentages per category. All summaries will be presented by treatment group, unless otherwise specified.

Baseline values for all parameters will be the most recent value prior to administration of study product or speculum exam.

All subject data will be presented in individual subject data listings. Unless otherwise stated, unscheduled visit results will be included in date/time chronological order, within patient listings only. All listings will be sorted by investigational site, patient number, and visit. The treatment group (AMPHORA, Placebo) as well as patient's age and sex (if available) will be stated on each listing. With respect to study tables, the mITT population will be used for efficacy analyses; safety population will be used for safety analyses.

